### 8.3 Aim III

The vascuCAP™ measurements will be used to classify the target lesions according to whether the analytes suggest it is not a plaque, or if it is, which of the 8 AHA types best fits the analyte profile. The data from the first phase will be used to build the classifier, and the data from second phase will be used as a first assessment of the accuracy of the classifier. This is considered a pilot study for the classifier and will not be included in the *Profiling* product release until sufficient statistical significance for all outputs is demonstrated.

With the limited sample size for the assessment of the classifier, we will not attempt to model the results. Rather, we will simply report the 9x9 table of AHA types by histopathology vs. AHA types by vascuCAP™'s classifier. In addition, for each of the AHA types according to histopathology, we will report:

1. the frequency with which vascuCAP™'s classification agrees with histopathology,
2. the frequency with which vascuCAP™'s classification is within an acceptable range (see Table 6), and
3. the frequency with which vascuCAP™'s classification is not within an acceptable range.

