**Final Assessments**

- I. Bias, precision, and reproducibility of each of the functional analytes as measured by vascuCAP™.
- II. Performance characteristics of the structural and hemodynamic analytes.
- III. Accuracy of vascuCAP™ classification of target lesion by AHA type.

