## 2.2 Rationale

We hypothesize that *in vivo* MRI examinations of patients, when suitably acquired and analyzed with the vascuCAP™ analysis software, can provide a sufficiently accurate profile of plaque characteristics to provide an objective basis for patient management.

We propose to use MRI to evaluate the extent, as well as, the structure, composition, and functional aspects of atherosclerotic plaques in  $\geq 110$  patients (80 carotid patients and 30 femoral patients) scheduled to undergo an endarterectomy of the aforementioned vascular beds as part of their routine clinical care. These patients will be undergoing endarterectomies to mitigate their clinical risk or symptoms for things such as strokes, claudication, and critical limb ischemia. The endarterectomy specimens removed at surgery will allow a direct comparison between the MRI information obtained prior to the surgery, and the histopathological analyses of the arterial specimens. All patients will undergo a MRI examination within 30 days of the surgical procedure. Histological samples will be analyzed to identify neovascularization, intra-plaque hemorrhage, collagen types, necrotic core, and other hallmarks of plaque severity.

Histology and MRI will be co-registered, step-sectioning through the endarterectomy specimen using the suture-marked proximal and distal ends and anterior face as the anatomical markers. We create ground truth maps from histology of the excised specimens with the pre-operative MRI. This allows for careful mapping of the precise extent of plaque from the corresponding pathologic lesion onto the *in vivo* imaging. This will allow for careful training and testing of the image based classifiers to identify and characterize the plaque regions. Study duration, from

IRB approval through analysis and close of study is expected to require approximately 18 months, with 12 months targeted for subject enrollment and acquisition of samples, and 6 months to complete analyses and reporting.

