#### 4 STUDY DESIGN

A two-phase study is proposed. In the first phase, 75 surgical patients will be recruited as part of a training set; aims I-II will be evaluated with this set. In the second phase, at least a minimum of 35 and as many as 75 surgical patients will be recruited (number to be set based on the results of a statistical analysis following the first phase). Data from the second phase will be used in the definitive results to be filed in a 510(k) application to the FDA documenting the statistical performance of vascuCAP™'s ability to measure functional and structural analytes according to Aims I and II. Data collected in the second phase will also be used as additional training data for Aim III.

vascuCAP™'s performance in measuring functional analytes will be assessed using histology of specimens collected during surgery as ground truth. vascuCAP™'s performance in measuring structural analytes will be facilitated by comparing its automated segmentations against manual contours produced independently by two radiologists recruited for the study. The two radiologists will independently perform the manual contouring for all study patients, and one of these two radiologists will also perform the vascuCAP™ aided contouring after a sufficient wash-out period after the manual contouring and with appropriate blinding to their manual results.

Patients are recruited, enrolled, and analyzed with vascuCAP™. 75 patients which have been imaged and on which surgery was performed within 30 days of imaging will form the training set. An analysis will be performed and revisions to vascuCAP™ will be made, as appropriate. The sample size for the *Profiling* will be determined at this time; we denote this as  $N_{\text{profile}}$ . After analysis, the product configuration will be locked, and subsequent patient results are blinded. After  $N_{\text{profile}}$  additional patients have been imaged and on which surgery was performed within 30 days of imaging ( $N_{\text{profile}} \geq 35$ ).

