## 8 STATISTICAL ANALYSIS

A two-phase study is proposed. In the first phase, 75 surgical patients will be recruited as part of a training set; aims I-III will be evaluated with this set. In the second phase, at least 35 surgical patients will be recruited (possibly more, depending on the results of the first phase). Data from the second phase data will be used in the 510(k) application (i.e. Report of the results of the performance of the functional and structural analytes) and as additional training data for Aim III.

Two radiologists will be recruited for the study. The two radiologists will independently perform the manual contouring for all study patients, and one of these two radiologists will also perform the vascuCAP™ aided contouring after a sufficient wash-out period after the manual contouring and with appropriate blinding to their manual results.

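### Could the phase-two lesions that first test the AHA plaque-type classifier already have been used to train it?

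*Combined protocol and SAP*

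**What the plan says.** Section 8.3, the section written for Aim III, divides the data by phase. On phase one: "The data from the first phase will be used to build the classifier". On phase two: "the data from second phase will be used as a first assessment of the accuracy of the classifier". The planned output is a nine-by-nine cross-tabulation of histology type against classifier type. For each histology type it adds the frequencies of exact agreement and of results inside and outside the acceptable range in Table 6.

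Two other places give phase two a second role. Section 4 states: "Data collected in the second phase will also be used as additional training data for Aim III". The opening of section 8 likewise lists phase-two data "as additional training data for Aim III".

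The same two places differ on phase one. Of the 75-patient training set, section 4 says "aims I-II will be evaluated with this set" and section 8 says "aims I-III will be evaluated with this set".

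Two further statements bear on the order of work. Section 4 freezes the product configuration after the phase-one analysis and keeps the results of later patients blinded. Section 3.2 sets all three endpoints, including the AHA classification, under a blinded comparison with histology.

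**The concern.** A data set cannot give an honest first test of a classifier if it has already helped to fit it. Read alone, sections 4 and 8 give phase two only a training role for Aim III; the testing role appears only in section 8.3. No sentence says that the cross-tabulation is produced before phase-two lesions join the training set. The configuration freeze in section 4 does not name the AHA classifier, and section 8.3 keeps that classifier out of the *Profiling* release, so one can doubt whether the freeze covers it. Section 8's wording on phase one adds to the doubt, because it could be taken to mean that Aim III accuracy is judged on the lesions that built the classifier.

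At stake is the only Aim III result planned. Accuracy of "classification of target lesion by AHA type" is the third of the final assessments in the protocol summary. With few lesions, many measurements and nine categories, scoring lesions already used in training can flatter a classifier considerably.

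**Working it through.** The plan states no sample size, power or accuracy target for Aim III, so there is no figure to reproduce. The check is mainly a reading of the passages together, with lesion counts to show the scale.

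**Lesion counts.** Section 8.1 gives the patient numbers and assumes one target lesion per carotid patient and two per PAD patient.

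- Phase one: 55 + 2 × 20 = 95 lesions.
- Phase two at its minimum: 25 + 2 × 10 = 45 lesions, or 45 / 9 = 5 per category on average.
- Pooled: 95 + 45 = 140 lesions, of which phase two is 45 / 140 = 32%.

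**Do the two roles of phase two conflict?** There are two possible orders.

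1. *Build on phase one, score phase two, then add phase two to training.* Phase one builds the classifier, phase two is its first assessment, and phase-two data are later available as extra training data. All three passages hold.
2. *Pool both phases, then score phase two.* Phase one alone no longer builds the classifier that is assessed, and the assessment is no longer a test on fresh lesions. This goes against section 8.3.

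Only the first order satisfies every sentence. In section 8.3 the cross-tabulation comes straight after the statement that phase two supplies the assessment, and it is justified by the small sample available for that assessment. The table therefore belongs to the phase-two test.

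**Does blinding help?** Training needs histology labels. Using phase-two labels before scoring would sit badly with the blinded comparison in section 3.2 and with the blinding of later results in section 4. Neither text names the order, so this supports the first reading without proving it.

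**What does evaluation on phase one mean?** Section 4 says Aims I and II are evaluated on the training set, yet takes their definitive results from phase two. In this plan, then, evaluation on phase one means development work. For Aim III, that work is building the classifier. Section 8.3 is part of section 8 and sets the held-out test explicitly, so the opening sentence of section 8 does not displace it.

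**How large would the bias be under the second order?** The documents give no classifier, mix of types or separation between types, so these must be assumed.

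- *Pure-noise measurements, nine equally likely types, linear discriminant, 95 training and 45 test lesions.* Scoring first gives about 11% agreement, which is chance (1 / 9 = 11%). Scoring after pooling gives about 24% with 6 measurements, 30% with 10, 41% with 18 and 45% with 22.
- *A wider set of 360 assumed settings.* Here bias is the accuracy of the pooled classifier on phase-two lesions minus its accuracy on new lesions. It ranged from 0.0 to 35.5 points: 0.0 to 2.4 when type means differ with an SD of 2 within-type SDs per measurement, and 4.1 to 34.5 when that SD is 0.3.

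These runs show that the order matters. They do not show which order the plan follows.

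**The case for a change.** The strongest case for a change is that the order is inferred. Two of the three passages that give phase two a role in Aim III mention only training, and a reader who followed them alone would use up the held-out lesions. Blinding must end before phase-two labels can train anything, and the plan does not say that the table is finished by then. Once the classifier has been shaped by those lesions, a clean first test may need new patients. Writing the order down would cost a sentence or two.

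Part of this stands. The order is not stated, the freeze does not clearly reach the classifier, and the two descriptions of phase one do differ. But the argument needs an analyst to set aside the section that specifies the Aim III analysis in favour of two summary sentences that do not contradict it. Someone working from section 8.3 would fit on phase one, tabulate phase two and only then retrain. The simulated figures do not strengthen the case, since they depend on assumed inputs and on the order that section 8.3 excludes.

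**Conclusion.** No change to the plan follows. The unstated order is a gap that analysts would fill sensibly, because building on phase one, scoring phase two and then retraining is the only sequence that satisfies sections 4, 8 and 8.3 together. Followed that way, the cross-tabulation and the Table 6 frequencies are a sound held-out assessment, with no bias from this source. The difference between Aims I and II in section 4 and Aims I to III in section 8 is a clerical slip that alters no planned result.

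The stakes are limited even if this reading were wrong. Aim III is a secondary objective. Section 8.3 calls it a pilot, reports it descriptively and withholds the classifier from the release until stronger evidence exists. Section 4 ties the 510(k) performance results to Aims I and II. No hypothesis test or sample size depends on the table.

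The conclusion rests on section 8.3 governing Aim III and on phase-two lesions being scored by the classifier built on phase one. If a report showed that phase-two lesions had entered training before they were scored, its accuracy figures should be read as optimistic by an amount the documents do not allow one to estimate.

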**Table 6: Penalty Matrix for Evaluating vascuCAP™ AHA Plaque Type Classifier**

Classification	Truth								
	0	1	2	3	4	5	6	7	8
0	A								
1	A	A							
2	NA	A	A						
3	NA	NA	A	A					
4	NA	NA	NA	A	A				
5	NA	NA	NA	NA	NA	A			
6	NA	NA	NA	NA	NA	NA	A		
7	NA	NA	NA	NA	NA	NA	NA	A	
8	NA	NA	NA	NA	NA	NA	NA	NA	A

A=acceptable

NA=not acceptable

